### **8.2.3. Sleep and Study Intervention Dosing Diaries**

Electronic sleep and study intervention dosing diaries will be completed by the participant daily for approximately 7 days around the time of (and including) each 24-hour BP recording. The sleep diary and the study intervention dosing diary will be completed on the same days. Therefore, the participant will complete a total of approximately 14 days of diary entries, including the days of each 24-hour BP recording.

Site personnel should initialize diaries at each study visit specified in the SoA and review diary data entries during the specified time period (approximately 7 days). Participants who are

missing diary entries should be contacted immediately by site personnel and encouraged to comply with diary entry requirements. Instances of participant noncompliance with diary entry requirements will be recorded as protocol deviations.

Refer to Section 6.5 and the SoA (Section 1.3) for additional details.

#### **8.2.4. Patient Global Impression of Severity**

The PGIs is a single-item 7-point Likert-type rating scale that is widely used in clinical studies to assess the severity of a condition. Using this scale, participants will be asked to rate the level of severity of each of the following: diaphoresis, nocturia, edema, and enuresis.

#### **8.2.5. Patient Global Impression of Change**

The PGIC is a 7-point Likert-type scale that is widely used to evaluate efficacy in clinical studies by assessing a participant's impression of response to treatment. Using this scale, participants will be asked to rate their impression of change for each of the following: diaphoresis, nocturia, edema, and enuresis.

### **8.3. Safety Assessments**

Planned time points for all safety assessments are provided in the SoA (Section 1.3).

#### **8.3.1. Physical Examinations**

A physical examination will be performed at Screening to include, at a minimum, upper arm circumference measurement (for the ambulatory BP monitoring cuff) and an abbreviated system review (head, eyes, ears, nose, and throat; chest; heart; lungs; abdomen; and extremities).

#### **8.3.2. Vital Signs**

##### **8.3.2.1. Blood Pressure and Other Vitals**

- BP and pulse measurements should be obtained at the investigational site using the sponsor-provided device (site-based participants) or at the participant's home location with study personnel using the sponsor-provided device (decentralized participants). The same device should be used for each measurement to ensure consistency for a given participant.
- BP and pulse measurements should be preceded by at least 5 minutes of quiet rest (ie, no talking) and obtained while the participant is seated in a quiet setting without distractions (eg, television, cell phones).
- BP and pulse measurements will be obtained using a sponsor-provided OBPM device. Once initiated, this device will start a 5-minute countdown (ie, a rest period), followed by 3 consecutive BP and pulse rate measurements with 1-minute intervals between each measurement. The device will then automatically calculate and record an average for the 3 BP and 3 pulse rate readings (calculated and recorded separately for SBP and DBP).

- At the Screening Visit, BP and pulse measurements should be obtained before blood collection for laboratory tests. BP and pulse may be repeated up to 2 additional times if the investigator considers that the average recorded by the device was unduly influenced by transitory factors (eg, excessive movement or loud noises during measurement). All screening measurements should be reviewed and filed in the source documents. The investigator will select only 1 recording average for purposes of study eligibility.

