### **Overall Rationale for the Amendment:**

The overall rationale for Amendment 04 was to increase the upper limit of the screening SBP required for eligibility from 145 to 155 mm Hg. This updated criterion will expand the study population, which was originally defined by a narrow SBP range, to subserve clinical homogeneity in the sample. The narrow range for eligible SBP, coupled with the higher-than-anticipated screen failure rate, has been a potential barrier to enrollment and prompted this amendment. Increasing the upper SBP limit to 155 mm Hg is consistent with eligibility criteria used in other studies assessing the impact of dietary sodium reduction on BP (eg, 159, 160 mm Hg; [Sacks, 2001](#); [Juraschek, 2017](#); [Gupta, 2023](#)). In addition, results of this study with an expanded SBP range are more likely to be representative of study populations that demonstrated an increased prevalence of hypertension in narcolepsy ([Ohayon, 2013](#); [Tessier-Sherman, 2013](#); [Black 2017](#); [Ben-Joseph, 2023](#)).

The eligibility criteria were also updated to clarify that participants must be taking high-sodium oxybate with twice-nightly dosing at study entry and exclude participants with resistant hypertension. In addition, the amendment includes 2 new laboratory tests (urine potassium and microalbumin) to supplement the interpretation of core data. Finally, the number of participants expected to enroll (ie, sign the ICF) was increased to align with the high observed screen failure rate. Additional changes were made throughout the protocol for operational clarity. A description of changes is provided below. Minor editorial changes have not been summarized in the table.

Section # and Name	Description of Change	Brief Rationale

 
1.1 Synopsis
 
3 Objectives, Endpoints, and Estimands
 
4.1 Overall Design
 
4.2 Scientific Rationale for Study Design
 
5.1 Inclusion Criteria
 
	The upper limit of the average screening SBP required for eligibility was increased from 145 to 155 mm Hg.	This change was made to support study recruitment. This update will expand the participant population for whom a switch from twice-nightly high-sodium oxybate to XYWAV may be relevant, as it includes a broader range of hypertension (ie, a screening SBP between 130 and 155 mm Hg [inclusive]).

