### 1.3. Schedule of Activities

**Table 3: Schedule of Assessments – Site-Based Participants**

Procedure	Screening Period (twice-nightly high-sodium oxybate)	Intervention Period (XYWAV) Telemedicine Visits shaded in gray						E/D	Safety Follow-up Visit	Notes
		Switch to XYWAV					End of Treatment Visit			
Study Visits	V1 a	V2	V3	V4	V5	V6	V7 a		V8	Additional unscheduled visits will be needed a .
Scheduled Day(s)	-14	1	7	14	28	35	42*		56**	*Study intervention to be taken each night until the EOT 24-hour BP assessment has met minimum data quality standards a . **SFU Visit should occur 14 days (+ 3 days) after the last dose of study intervention or E/D Visit (as applicable).
Study Visit Window (days)	-7 (ie, Day -21)		± 3	± 3	± 3	± 3	± 3		+ 3	
Informed consent	X									
Inclusion/exclusion criteria	X	X								Confirm that participant continues to meet eligibility criteria and that screening 24-hour BP measurement meets quality control criteria before switching to XYWAV.
Demographics	X									
Medical history	X									
Physical examination	X									Refer to Section 8.3.1.
Vital signs (OBPM, pulse, height, weight)	X*			X	X		X	X		Triplicate OBPM and pulse rate recordings are collected and averaged automatically using the sponsor-provided device. *At the Screening Visit, triplicate OBPM and pulse rate recordings may be repeated up to 2 additional times (Refer to Section 8.3.2). *Height only required at screening.
Electrocardiogram	X						X	X		
Clinical labs	X									
Serum pregnancy test (WOCBP only)	X									Serum test at screening as assessed by a central laboratory.
Urine pregnancy test (WOCBP only)		X					X	X		Urine tests (dipstick) may be performed at additional study visits, if needed.

Procedure	Screening Period (twice-nightly high-sodium oxybate)	Intervention Period (XYWAV) Telemedicine Visits shaded in gray						E/D	Safety Follow-up Visit	Notes
		Switch to XYWAV					End of Treatment Visit			
Study Visits	V1 a	V2	V3	V4	V5	V6	V7 a		V8	Additional unscheduled visits will be needed a .
Scheduled Day(s)	-14	1	7	14	28	35	42*		56**	*Study intervention to be taken each night until the EOT 24-hour BP assessment has met minimum data quality standards a . **SFU Visit should occur 14 days (+ 3 days) after the last dose of study intervention or E/D Visit (as applicable).
Study Visit Window (days)	-7 (ie, Day -21)		± 3	± 3	± 3	± 3	± 3		+ 3	

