24-Hour urine collection	X						X	X		Should occur within 72 hours of the 24-hour BP recording (can be extended to 1 week if necessary). Must occur (but results do not need to be available) before the switch to XYWAV.
24-Hour BP monitoring a	X						X	X		
 
Screening recording should occur after all eligibility criteria are met (but laboratory results do not need to be available) and ≤ 2 weeks prior to the switch to XYWAV.
 
Participants must return device within 3 days after the conclusion of the recording (which will require an additional site visit).
 
Refer to Section 8.2.1.
 

Participant instructions	X	X	X	X	X	X	X	X	X	
Sleep diary	X					X	X	X		
 
To be completed daily for approx 7 days around the time of (and including) each 24-hour BP recording.
 
To be completed concurrently with the study intervention dosing diary.
 
Site personnel should initialize diary at each specified visit and review diary data entries during each approx 7-day period.
 
Refer to Section 8.2.3.
 

Procedure	Screening Period (twice-nightly high-sodium oxybate)	Intervention Period (XYWAV) Telemedicine Visits shaded in gray						E/D	Safety Follow-up Visit	Notes
		Switch to XYWAV					End of Treatment Visit			
Study Visits	V1 a	V2	V3	V4	V5	V6	V7 a		V8	Additional unscheduled visits will be needed a .
Scheduled Day(s)	-14	1	7	14	28	35	42*		56**	*Study intervention to be taken each night until the EOT 24-hour BP assessment has met minimum data quality standards a . **SFU Visit should occur 14 days (+ 3 days) after the last dose of study intervention or E/D Visit (as applicable).
Study Visit Window (days)	-7 (ie, Day -21)		± 3	± 3	± 3	± 3	± 3		+ 3	
Study intervention dosing diary	X					X	X	X		
 
Before the switch to XYWAV (ie, at screening), diary will capture the use of twice-nightly high-sodium oxybate.
 
To be completed daily for approx 7 days around the time of (and including) each 24-hour BP recording.
 
To be completed concurrently with the sleep diary.
 
Site personnel should initialize diary at each specified visit and review diary data entries during each approx 7-day period.
 
Refer to Section 6.5 and Section 8.2.3.
 

C-SSRS	X									Administered by qualified site rater.
PGIs	X						X	X		
PGIc							X	X		

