#### Type of Participant and Disease Characteristics

2. Participants have a documented diagnosis of Type 1 or Type 2 narcolepsy that meets ICSD-3 or DSM-5 criteria.
3. Participants must have been receiving a total dose of high-sodium oxybate (eg, XYREM) of 6 to 9 g/night (inclusive) with twice-nightly dosing for a minimum of 6 consecutive weeks prior to screening.
4. If currently treated with stimulants and/or alerting agents or other medications known to affect BP, participant must have been taking the same dosing regimen for at least 2 months prior to screening and agree to take the same dose throughout the study.
5. If currently taking stable doses of antihypertensive therapies, participant must maintain these treatments at the same dose throughout the study unless otherwise advised by their medical care provider. Also refer to exclusion criterion 12.

Note: For inclusion criteria 6 and 7, BP measurements will be collected using a device provided by the sponsor as described in Section 8.3.2.1. Participants with resistant hypertension are excluded (refer to exclusion criterion 12).

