## 5.2. Baseline and Study Day Definitions

### 5.2.1. Baseline

In this study, the screening period includes all measurements taken after informed consent is obtained until Day 1. Baseline refers to the most recent observation prior to Day 1.

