## 5.4. Level of Significance & Multiplicity Adjustment

To control family-wise error rate inflation due to multiple endpoints and the interim analysis (Section 3.5), a fixed hierarchical testing sequence will be employed. Testing begins with the first endpoint at the specified alpha level and continues through the sequence until an endpoint is not statistically significant. Remaining analyses will be considered exploratory and associated p-values will be considered nominal.

The Type I error rate for study endpoints will be set at a one-sided level of 0.025. To account for the possibility of ending the study at the interim analysis, statistical significance for the primary endpoint (#1) will be assessed using O'Brien-Fleming one-sided alpha levels of 0.00998 for the interim analysis and 0.02194 for the final analysis. Statistical significance for each of the secondary endpoints (#2 to #4) will be assessed using the Pocock one-sided alpha level of 0.0168 at either the interim or final analysis.

Statistical hypotheses to be tested (in sequential order):

1. Change in the 24-hour average SBP (mm Hg) following 6 weeks of XYWAV treatment after switching from high-sodium oxybate in participants with narcolepsy
2. Change in the daytime average SBP (mm Hg) following 6 weeks of XYWAV treatment after switching from high-sodium oxybate in participants with narcolepsy
3. Change in the seated resting average SBP (mm Hg) following 6 weeks of XYWAV treatment after switching from high-sodium oxybate in participants with narcolepsy
4. Change in the nighttime average SBP (mm Hg) following 6 weeks of XYWAV treatment after switching from high-sodium oxybate in participants with narcolepsy

Analyses not part of this hierarchy will be considered exploratory, and no multiplicity adjustment will be performed. P-values reported in standard table outputs will be considered nominal.

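### The seated SBP baseline comes from the screening readings that decide eligibility, so regression to the mean can bias hypothesis 3 by an amount the documents do not fix (about 0.9 to 4.2 mm Hg under stated assumptions)

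*Protocol*

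**What the plan says.** **Eligibility.** The note in Protocol 5.1 ties the blood-pressure criteria to the seated office device: "For inclusion criteria 6 and 7, BP measurements will be collected using a device provided by the sponsor as described in Section 8.3.2.1". The text of criteria 6 and 7 is not shown, so the window is taken from the summary of changes for the current Amendment 04, which gives "a screening SBP between 130 and 155 mm Hg [inclusive". Protocol 8.3.2.1 adds that "BP and pulse may be repeated up to 2 additional times if the investigator considers" the device average to have been distorted by transitory factors, and then: "The investigator will select only 1 recording average for purposes of study eligibility".

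**Schedule.** In Protocol Tables 3 and 4 the vital-signs row has one entry before the switch, at Visit 1, and none at Visit 2. Later readings are at Visits 4, 5 and 7 and early discontinuation (site-based), or at Visit 7 and early discontinuation (decentralized).

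**Baseline.** SAP 5.2.1: "Baseline refers to the most recent observation prior to Day 1". Protocol 9.3.1.1 has the same rule.

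**Testing.** Third in the fixed sequence of SAP 5.4 is "Change in the seated resting average SBP (mm Hg) following 6 weeks of XYWAV treatment after switching from high-sodium oxybate", at a one-sided level of 0.0168, after 24-hour and daytime SBP and before nighttime SBP.

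**Analysis.** Protocol 9.3.3 and SAP 7.2.1 apply the primary method: ANCOVA of change on mean-centred baseline. Protocol 4.2 states that no control group is needed. Protocol 9.3.2 describes the centring as a computational convenience and cites a paper on regression to the mean in support of it.

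**The concern.** A participant enters only if a seated reading at screening falls inside the window. If the population screened has a mean below the middle of that window (142.5 mm Hg), those who qualify include a surplus of people whose reading happened to be high that day. Their next reading is lower on average without any treatment. Here the truncated visit supplies the baseline, and nothing in the design separates the resulting fall from a drug effect. Protocol 4.2 justifies the lack of a control by arguing that blood pressure would not be expected to change much over six weeks. Selection on the baseline visit breaks that argument for this endpoint.

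At stake are a formal claim for seated SBP whose error rate may be far above 0.0168 and, if there is a real seated fall, an overstated estimate of it in a study whose aim is to quantify the change.

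The ambulatory endpoints do not share the direct problem. Protocol 8.2.1 starts the screening recording only after the other criteria have been assessed and met, and that recording is not itself truncated.

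**Working it through.** **1. The plan's own figure.** A one-sample t-test at one-sided 0.025, difference 3.5, SD 8.0 and N = 57 gives power 90.1%, as planned. All 18 cells of Protocol Table 6 reproduce. These inputs are for 24-hour SBP; none are given for seated SBP.

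**2. The model does not remove the bias.** With one arm and a covariate centred at its sample mean, the least-squares intercept is the mean of the dependent variable. The LS-mean therefore equals the raw mean change from baseline. Simulation confirmed the identity.

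**3. Size of the bias.** Let the source population have mean μ, between-person SD σb and visit-to-visit SD σw, with normal distributions and independent visits. Then

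expected fall = (1 − R) × (E[X | 130 ≤ X ≤ 155] − μ), where R = σb² / (σb² + σw²).

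Worked case, μ = 125, σb = 12, σw = 8: total SD = √(144 + 64) = 14.42; 1 − R = 64/208 = 0.308; truncated mean = 138.76. Fall = 0.308 × 13.76 = 4.2 mm Hg.

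The rejection rates come from simulating the planned ANCOVA with n = 57, no seated effect and one-sided 0.0168 (10,000 replicates; Monte Carlo error about half a percentage point).

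| Assumed μ | σb / σw | 1 − R | Truncated mean | Spurious fall (mm Hg) | Test alone rejects |
|---|---|---|---|---|---|
| 125 | 12 / 6 | 0.200 | 138.3 | 2.7 | 63% |
| 125 | 12 / 8 | 0.308 | 138.8 | 4.2 | 81% |
| 125 | 14 / 6 | 0.155 | 139.1 | 2.2 | 45% |
| 125 | 14 / 8 | 0.246 | 139.4 | 3.5 | 64% |
| 130 | 12 / 6 | 0.200 | 139.4 | 1.9 | 34% |
| 130 | 12 / 8 | 0.308 | 139.8 | 3.0 | 51% |
| 130 | 14 / 6 | 0.155 | 140.0 | 1.6 | 24% |
| 130 | 14 / 8 | 0.246 | 140.2 | 2.5 | 36% |
| 135 | 12 / 6 | 0.200 | 140.6 | 1.1 | 14% |
| 135 | 12 / 8 | 0.308 | 140.8 | 1.8 | 20% |
| 135 | 14 / 6 | 0.155 | 141.0 | 0.9 | 10% |
| 135 | 14 / 8 | 0.246 | 141.1 | 1.5 | 15% |
| 140 | 12–14 / 6–8 | 0.155–0.308 | 141.9–142.0 | 0.3–0.6 | 3–5% |

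**4. A smaller variance.** The visit SDs above imply an SD of change of 6√2 = 8.5 to 8√2 = 11.3, more than the 7 to 8 that the plan uses for 24-hour SBP. Carrying the plan's 7 to 8 over, with between-person SD 10 to 14, gives 1.5–3.0 mm Hg at mean 125, 1.1–2.1 at 130, 0.7–1.2 at 135 and 0.2–0.4 at 140. With between-person SD 12 and SD of change 8, the test alone rejects 58%, 31%, 13% and 4% of the time at those four means.

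**5. With a separate baseline.** If baseline is a second reading taken after qualification, the same model (between-person SD 12, SD of change 8) gives an expected fall of 0.0 mm Hg at every source mean from 120 to 140. The rejection rate becomes 2.5% to 3.1%. What remains above 1.7% is not regression to the mean: the ANCOVA standard error leaves out sampling variation in the baseline mean, which is a separate matter.

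**6. Which reading is the baseline when there are repeats?** SAP 5.2.1 points to the last one. SAP 5.2.3 takes the latest result within a visit window, but for two observations on the same day it takes the one with the earliest time. Triplicates repeated at the Screening Visit fall under both rules.

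**The case against.** The strongest reply is that the size is not in the documents, and much of it stands.

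- **Comparison with 3.5 mm Hg.** A reader might infer that regression to the mean alone yields a fall as large as the hypothesised effect. In the table it reaches 3.5 only at source mean 125 with visit SD 8. The figure also belongs to 24-hour SBP; no effect is specified for seated SBP.
- **The largest scenarios fit the plan least well.** At mean 125, about 65% of those screened would miss the window on a single reading, against a planned screen-failure rate of 60% for all causes. Means of 130 to 135 imply 42% to 56%. Repeats and rescreening could narrow this gap.
- **Gatekeeping.** A reader might infer that hypothesis 3 is likely to succeed even if the drug does nothing. The documents do not support that: seated SBP is tested only after 24-hour and daytime SBP have both succeeded, so with no effect on any endpoint the nominal chance of reaching it is at most about 2.5%. The rates above are for the seated test alone.
- **Nighttime SBP.** A wrongly passed hypothesis 3 lets nighttime SBP be tested, but at its own 0.0168 and on an ambulatory baseline. Its own test level is not inflated.
- **Choice among repeats.** A reader might assume that the investigator's chosen reading is always the baseline. With repeats it need not be (step 6). Any candidate is still from the same visit, so the bias may shrink but need not vanish.

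The structure does not depend on the assumptions: one truncated visit supplies the baseline, with no control and an estimate equal to the raw change. Gatekeeping also gives no protection in the case that matters, when ambulatory SBP has met its tests.

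**Conclusion.** The point holds as a bias of certain origin and uncertain size. Under the main assumptions (source mean 125 to 135, between-person SD 12 to 14, visit SD 6 to 8 mm Hg, independent normal visits), the spurious fall is about 0.9 to 4.2 mm Hg and the seated test alone rejects about 10% to 80% of the time with no seated effect. At a source mean of 140 these become 0.3 to 0.6 mm Hg and about 3% to 5%. The fall may approach the 3.5 mm Hg planned for 24-hour SBP, but it need not. Investigator choice among repeats and the one permitted rescreen were not modelled.

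The consequence is limited to seated SBP once hypotheses 1 and 2 have succeeded: a false claim, or an overstated real fall. The primary endpoint is not affected by this mechanism. This should be fixed, but it does not undermine the main result.

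**What to change.** By protocol amendment and SAP revision:

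1. **Separate baseline for participants not yet switched.** Take one triplicate office reading that plays no part in eligibility, at the in-person contact where the screening ambulatory device is returned (site-based) or staff come back for it (decentralized). Protocol Tables 3 and 4 already require that contact, within 3 days after the recording, and recording quality must be confirmed before the switch. Define this reading as the seated baseline in Protocol 9.3.1.1 and SAP 5.2.1.
2. **Formal sequence.** Participants already switched cannot supply that reading. Remove seated SBP, leaving 24-hour, daytime, then nighttime SBP, or at least place it last. Report it descriptively with a caveat on regression to the mean, and show participants with the new baseline separately.
3. **Repeats.** State which screening reading serves as baseline when there are several, and reconcile SAP 5.2.1 with the two rules in SAP 5.2.3.

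The cost is a short extra measurement at an existing contact, an amendment with the usual ethics and authority approvals, and one fewer confirmatory claim if seated SBP leaves the sequence.

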#### **8.3.2.2. Height and Weight**

- Height and weight will be measured and recorded at the time points indicated in the SoA (Section 1.3).
- Weight should be measured at the investigational site (site-based participants) or at home using a digital scale brought to the participant's location by study personnel (decentralized participants). The same device should be used for each measurement to ensure consistency for a given participant.

